Overview. Similar to Project 1, this project is a hybrid type III effectiveness-implementation design using a stepped-wedge design and mixed methods evaluation. We will test two implementation strategies, REP alone versus REP+CONNECT for implementation of iHI-FIVES.⁴⁵ The type III design was selected for three reasons: the implementation strategy REP and implementation interven-

Table 5. HI-FIVES Curriculum CORE: 4 IN-PERSON WEEKLY GROUP CLASSES Session 1: Introduction, frustrations and rewards of CG Session 2: Clinical issues, increasing independence, prevent injury Session 3: Caring for the caregiver, communication, depression, burnout Session 4: Navigating the VHA, planning for future, services for CGs OPTIONAL: 1-3 PHONE TRAINING CALLS, caregivers choose topics, action items Patient-oriented topics a. Disease information d. Managing symptoms at home b. Safety issues such as falls e. Planning for future (directives) c. Safe home environment, driving f. Sleep hygiene for patient Caregiver-oriented topics a. Management of stress d. Sleep hygiene for self e Coping with frustrations b. Caring for self f. Relaxation techniques c. Asking for help OPTIONAL: 1-2 BOOSTER CALLS, after group classes, general check-in and follow up on any action items

tion CONNECT have strong preliminary evidence;^{24,44} iHI-FIVES shows promise in evaluations of 'value' to CGs through increasing caregiver perceived quality and satisfaction with VHA care the Veteran receives; and the VA Caregiver Support Program views iHI-FIVES to hold great promise to fill critical gaps in training for CGs of cognitively or functionally impaired Veterans. To improve the evidence-base for iHI FIVES across multiple sites, we will carefully track both patient-level clinical effectiveness and site-level implementation outcomes.

The participants in the iHI-FIVES clinical program will be CGs of Veterans who had a recent referral (3 months or 6 months) to receive Veteran directed care or home and community-based services (home-based primary care, homemaker home health aide services, adult day health care, respite care). ¹¹⁰ In addition, sites will use their discretion to recruit other caregivers who may benefit from their program, after receiving training in the REP process on the targeted caregivers of interest (e.g., those CGs helping functionally or cognitively impaired Veterans who are at high risk of nursing home entry).

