Key covariates. Patient-level covariates will be identified based on the ICF (Figure 1) and other factors known to assess independence including age, race, ethnicity, marital status, service connection, urban/rural status, NOSOS score from year prior to start date. Site-level covariates to explore will include presence of a Geriatric Research Education and Clinical Center, rural status, and academic affiliation. Data sources will include CDW, Inpatient Evaluation Center (IPEC), Strategic Analytics for Improvement and Learning (SAIL), Geriatrics and Extended Care Data Analysis Center (GECDAC) and the patient medical record.

Sample of Patients. Administrative data and VA/CMS Repository data will be used to construct the primary patient outcome. Analysis will be performed on a sample of Veterans from a 3 or 6-month repeated automated CDW data pull and/or VistaWeb/Joint Legacy Viewer as appropriate. This data pull will occur at a uniform time period (e.g., 2 weeks) of each 3 or 6-month interval for the duration of the 30-month study.

Patient eligibility criteria includes a consult or referral in the past 3 or 6-months from the date of the data pull to the following VA services:

- H/HHA (homemaker home health aide services)
- Home based primary care (HBPC)
- Adult day health care
- Respite care
- Veteran directed care

and meet none of the exclusion criteria:

• Consult or referral to hospice care.

We anticipate that there will be between 15,000 -18,000 total Veteran patients meeting these criteria. We will require sites have a minimum of 50 recent referrals to HCBS (recent is defined as within a 3 or 6-month interval) to be an eligible site.

Sample of Caregivers. Survey data will be used to construct secondary caregiver outcomes.

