To address if caregivers who participate in iHI-FIVES have higher satisfaction with VA care, lower depressive symptoms, and lower burden, analysis will be conducted at the level of the patient or caregiver utilizing all available data to evaluate iHI-FIVES effectiveness versus control condition on defined count and continuous outcomes. The overall anticipated sample size of eligible caregivers in the iHI-FIVES study will be 320. We will use random effect linear (continuous outcomes), negative binomial (count outcomes), or logistic (dichotomous outcomes) models appropriate for the stepped-wedge design which account for the correlation of patients within the same VAMC.^{34,60} For example with a continuous outcome, I VAMCs, T time points, N individuals per VAMC per time interval, the model is: $Y_{ijk} = \mu + \alpha_i + \beta_j + X_{ij}\theta + e_{ijk}$, where α_i is the random effect for the ith VAMC, β_j is a fixed effect that captures time trends, and X_{ij} is an indicator of the intervention mode for the ith hospital at time j (=0 prior to intervention and =1 post intervention), and θ is the measure of the effect of the intervention. Adjustments for patient characteristics and a random effect for VAMC site may also be added.

Sensitivity analysis. In addition to the primary analysis of the primary and secondary outcomes described above, we will perform an "as treated" analysis focused on the outcomes of Veteran patients from caregivers in the post-implementation period exclusively. This will show us whether there is benefit conferred upon those caregivers/Veterans in the iHI-FIVES program compared to similar caregivers/Veterans not in the program. The treated caregivers will be all caregivers who meaningfully participated in the iHI-FIVES training (e.g., attended at least one class). The comparison caregivers will be selected from the full set of caregivers referred to iHI-FIVES using n:1 matching on key baseline covariates of the patient and caregiver. The rationale for matching on key Veteran baseline covariates is to ensure that we have similar Veteran acuity in both groups, because the training may be differentially effective for caregivers by level of Veteran disability. Candidate matching variables for the patient include:

- Patient age bands
- Patient Jen Frailty Index Score (0-10)
- Patient CAN scores (1 year inpatient use version)
- Dementia status based on ICD9 codes in the past 6 months
- Documentation of incontinence in the past 6 months

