Sample size estimate. For STRIDE, sample size calculations were conducted for patient-level analyses evaluating impact of STRIDE on discharge to skilled nursing facility. The sample size calculation was done based on a complete stepped-wedge design using Hussey and Hughes (2007) method.⁶⁰ The sample size is based on the following assumptions for the discharge to skilled nursing facility outcome: 1) base discharge rate to skilled nursing of approximately 20%; 2) 10% drop in discharge rate after STRIDE, determined as a clinically significant gain in the outcome; 3) intracluster correlations (ICC) ranging from 0.02 to 0.6 for patients within the same hospital; 3) 8 hospital sites with 5 3-month assessment periods; and 4) alpha=0.05, power>80%. A total sample of 2000 patients (~250 per hospital, 50 per 3-month interval) will result in ≥80% power to detect a 10% reduction in discharges to skilled nursing facilities. The anticipated maximum sample is 16,000. For iHI-FIVES, the sample size calculation was done based on a complete stepped-wedge design using Hussey and Hughes (2007) method.⁶⁰ The overall anticipated number of Veteran patients will be 15,000-18,000 with a minimum sample size of 400 subjects (at least 50 per VAMC, 20 per 6-month interval). The power calculation for this sample size is based on the following assumptions for days not at home: 1) 8 is the baseline mean number of days not at home over 6 months; 2) 2-day reduction in days not at home over 6 months; 3) coefficient of variation (CV) ranging from 0.3 to 0.5 for assessments on participants within the same VAMC; 4) 8 VAMCs with five 6-month assessment intervals; and 5) alpha=0.05, power>80%. A minimum sample of 400 Veterans will result in at least 80% power to detect a mean reduction of 2 days not home assuming variance equal to the mean (Poisson distribution).

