Impact. Prevention of hospitalization-associated disability is an urgent clinical priority for VHA and Veterans. By implementing STRIDE in eight VAMCs, this project will fill this key gap in inpatient care for the more than 30,000 Veterans hospitalized in these facilities annually. In addition to important positive effects on Veterans' health and satisfaction we anticipate important budgetary impact through reduction in non-VA care costs for hospitalizations at non-VA facilities due to diversion status and reduced direct costs for post-acute institutional care. Finally, testing REP alone and REP + CONNECT will inform dissemination efforts. If the lower budget impact strategy of REP alone has the equivalent impact on individual outcomes, it may be preferred over REP + CONNECT.

Implementation of iHI-FIVES is expected to increase quality of care for vulnerable Veterans by better supporting the caregivers who care for them. In turn, better supporting caregivers can avoid costly nursing home placements. Importantly, the implementation of iHI-FIVES targets a prevalent, heterogeneous patient population at high risk of nursing home entry—keeping these vulnerable patients independent meets the definition of patient-centered care.¹²¹ Further, the focus on CONNECT and team-building aims to improve information flow about high-risk patients through the creation of new, cross-service teams. Increased information flow may enhance targeting of services to patients at highest risk of negative outcomes. And yet, if REP has similar impact on individual outcomes, it provides a lower budget impact option to CONNECT and will inform dissemination efforts. The project may also create positive practice spillovers by increasing provider knowledge about VA Caregiver Support Program.

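### The iHI-FIVES primary cohort is re-selected by home-care referral after each site switches, with no committed case-mix adjustment, so a change in who is referred would bias the days-not-at-home estimate

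*Combined protocol and SAP*

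**What the plan says.** **Cohort.** Under iHI-FIVES, Sample of Patients: "Analysis will be performed on a sample of Veterans from a 3 or 6-month repeated automated CDW data pull", and "Patient eligibility criteria includes a consult or referral in the past 3 or 6-months from the date of the data pull". Five home- and community-based services qualify, and hospice referral excludes. The same automated rule applies before and after go-live.

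**Possible routes to a changed cohort.**
- The text on barriers to caregiver training says that PACT and other providers will be educated about the Caregiver Support Program.
- Table 5 lists as a core class: "Session 4: Navigating the VHA, planning for future, services for CGs".
- The Impact section, writing about CONNECT, says: "Increased information flow may enhance targeting of services to patients at highest risk of negative outcomes".

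**Adjustment.**
- Key covariates (iHI-FIVES) lists age, race, ethnicity, marital status, service connection, urban/rural status and prior-year NOSOS. It does not list prior days not at home.
- The primary-outcome paragraph of Aim 2b discusses candidate distributions and commits to no covariate.
- The next paragraph opens on caregiver outcomes but describes analysis at patient or caregiver level. It says: "Adjustments for patient characteristics and a random effect for VAMC site may also be added".

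**Checks.** No section plans to compare home-care referral volume or case mix before and after go-live.

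**The concern.** In a stepped wedge with repeated cross-sections, the control and intervention samples should differ only by exposure, calendar time and site. Here the sampling criterion is a clinical act by staff whom the programme trains and informs. If go-live brings in milder Veterans, the post-implementation mean falls without benefit. If it brings in frailer Veterans, the mean rises and hides benefit. Either change would start at each site's own switch and so coincide with the intervention indicator. A large sample makes such a bias easier to mistake for an effect, because the standard error shrinks and the bias does not.

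**Working it through.** **Inputs from the documents.** Sample size estimate: "8 is the baseline mean number of days not at home over 6 months", a 2-day reduction, CV 0.3-0.5, 8 VAMCs, five intervals, variance equal to the mean, minimum 400 Veterans, alpha 0.05 (two-sided assumed, since sidedness is not stated). Sample of Patients: 15,000-18,000 Veterans. Study timeline: two blocks of two waves, two sites each, read as four steps, so 20 of 40 site-intervals are exposed (the shading of Figure 5 cannot be read).

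**Assumptions, not in the documents.** Extra referrals r = 10-30%; mean m of the added Veterans 3 or 16 days; within-site variance 100, 200 or 400 for the overdispersed case.

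**1. The plan's own figure.** The plan uses a "complete stepped-wedge design using Hussey and Hughes (2007) method". With I = 8, T = 5, U = 20, W = 0+4+16+36+64 = 120 and V = 2(16+9+4+1) = 60:

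Var = I s²(s² + Tτ²) / [(IU − W)s² + (U² + ITU − TW − IV)τ²], where s² = variance/n and τ = CV × 8.

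At 400 Veterans, n = 10 per site-interval and s² = 8/10 = 0.8.
- CV 0.3 (τ² = 5.76): 8(0.8)(29.6)/[40(0.8) + 120(5.76)] = 189.44/723.2 = 0.262; SE 0.512; power 97.4%.
- CV 0.5 (τ² = 16): 517.12/1952 = 0.265; SE 0.515; power 97.3%.

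The stated power of at least 80% holds under Poisson variance, so sample size is not the issue here.

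**2. Shift in the cohort mean with no true effect.** Δ = (8 + r·m)/(1 + r) − 8.

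| Extra referrals | m = 3 | m = 16 |
|---|---|---|
| 10% | 8.3/1.1 − 8 = −0.45 | 9.6/1.1 − 8 = +0.73 |
| 20% | 8.6/1.2 − 8 = −0.83 | 11.2/1.2 − 8 = +1.33 |
| 30% | 8.9/1.3 − 8 = −1.15 | 12.8/1.3 − 8 = +1.85 |

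**3. Why the model does not absorb it.** The model shown in Aim 2b has a site effect α_i, a period effect β_j and X_ij·θ. If the shift Δ starts at the switch and stays constant, the cell mean is μ + α_i + β_j + X_ij(θ + Δ). The site effect is constant over time and the period effect is common to all sites, so the analysis estimates θ + Δ.

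**4. Consequence at the anticipated size.** 15,000/40 = 375 per site-interval. With CV 0.4, the SE is 0.30, 0.42 and 0.59 for variance 100, 200 and 400. Normal-approximation rejection rates are:

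| True effect, shift | Var 100 | Var 200 | Var 400 |
|---|---|---|---|
| None, 0.4-day fall | 27% | 16% | 10% |
| None, 0.8-day fall | 77% | 48% | 27% |
| None, 1.2-day fall | 98% | 82% | 53% |
| 2 days, unmasked | >99% | >99% | 92% |
| 2 days, masked by 1 day | 92% | 66% | 39% |

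**5. What a full 2 days would need.** To produce a 2-day fall from nothing, the new share p of the post-go-live cohort must satisfy p(8 − m) = 2. At m = 3, p = 40%, which is 0.40/0.60 = 67% extra referrals. At m = 0, p = 25%, or 33% extra. Both exceed the assumed range. To cancel a true fall to 6, when the added Veterans get no benefit, p(m − 6) = 2. At m = 16, p = 20%, or 25% extra.

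**6. Scale.** Half of 15,000-18,000 is 7,500-9,000 post-go-live Veterans. Within those totals, 10-30% extra means 7,500 × 0.1/1.1 = 680 to 9,000 × 0.3/1.3 = 2,080 added Veterans. The caregiver Enrollment procedures mention a pool of 320 participating caregivers, which is 3.6-4.3% of that cohort.

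**The case against.** **The mechanism is inferred.** Provider education concerns the Caregiver Support Program, not home-care referral. Training is offered after the qualifying referral, so the targeted Veterans are already in the cohort. The Impact sentence says only that targeting may improve, and it follows text on CONNECT, which half the sites receive. This stands: the documents establish exposure to the bias, not the bias itself. It does not remove the concern, because provider and team activities act at site level and a family trained in one interval can re-qualify in a later pull.

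**The programme is too small to move referral this far.** Caregiver classes with about 320 participants could hardly generate 680-2,080 referrals. A shift of that size would need changed provider behaviour that no section describes. But limited reach also limits the signal. If only 320 participants benefit and they average 8 days, removing every one of those days lowers the cohort mean by 320 × 8/9,000 = 0.28 to 320 × 8/7,500 = 0.34 day. Some 6-7% extra referrals averaging 3 days would do the same.

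**Adjustment is not simply optional.** The permissive sentence sits in a mainly caregiver paragraph, and NOSOS is already a listed patient covariate. The accurate criticism is that the list is not tied to the primary model.

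**The as-treated analysis is a safeguard.** It uses post-implementation data only and matches on frailty and related measures, so a before-after referral shift does not drive it. It has its own selection limits and does not protect the primary estimate.

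**A stronger reading.** A reader might infer that a referral shift could manufacture the whole 2-day effect. The documents do not support that: the largest spurious fall in the assumed range is 1.15 days.

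**Conclusion.** The point holds as a risk of bias that is cheap to reduce. The primary cohort is selected partly after exposure, the primary model commits to no case-mix adjustment, and no check for a shift is planned. Under the assumed 10-30% extra referrals, the bias is a spurious fall of 0.45-1.15 days or a rise of 0.73-1.85 days, against a 2-day target. These sizes rest wholly on assumed shares and subgroup means, and on a shift that starts at the switch and persists.

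Complete masking of a true 2-day benefit falls inside the assumed range only near its upper end (25% extra referrals averaging 16 days and gaining nothing). Its direction rests on one tentative sentence in the Impact section. Nothing in the documents shows that referral will change in either direction.

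**What to change.** 1. Reconcile Key covariates with the two Aim 2b paragraphs. Make adjustment of the primary days-not-at-home model mandatory for the listed patient covariates, including NOSOS, and for days not at home in the 6 months before the qualifying referral. Build the latter from the same CDW/CMS data, and report the unadjusted model alongside.
2. Anchor that look-back at the qualifying referral, not at day 0. A 6-month window ending at day 0 lies wholly after go-live from each site's second post-implementation cohort onward, and can include time after the caregiver was trained on the index referral.
3. Report referral counts and mean NOSOS by site and period, and test each against X_ij in the same stepped-wedge model. With eight sites, give the interval and do not treat a non-significant result as reassurance.
4. Do not rely on a sensitivity analysis limited to Veterans referred before go-live. The outcome period starts at the end of month 3 of a block, and Participating Sites prefers a 3-month look-back. If the pull is at that point, every referral in a site's first post-implementation cohort falls after go-live and the restricted sample is empty. Run it only with the 6-month look-back, and apply the same referral-age restriction to the pre-implementation cohorts.

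**Cost.** SAP wording and modest extra data work: the look-back reaches at most 6 + 6 = 12 months before day 0. No new patients or procedures. The covariate keeps slight post-exposure contamination for Veterans who re-qualify in a later pull, and adjustment cannot remove unmeasured differences.

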Enrollment procedures. Of the Veteran patients identified from the repeated automated data pull described above to create the administrative primary outcome, we will mail introductory recruitment/opt-out letters signed by the PI (see Sample Letter for iHI-FIVES; Appendix). Patients will be provided a toll-free number to opt out. Starting about one week after mailing recruitment letters, a member of study staff will call patients and describe that we would like to conduct a brief survey with their family or friend caregiver by phone. If they do not have a caregiver, contact will cease. If they do, study staff will ask the Veteran patient for permission to contact the caregiver, and if allowed, will confirm contact information for the caregiver. The patient's interaction with the study team is limited to agreeing or declining to give the study team permission to contact their caregiver. See Appendix for the iHI-FIVES patient screening script.

Because the Veteran patient contact screening is entirely telephone based and minimal risk, we will seek a waiver of informed consent and of HIPAA, as approved by the Durham VAMC IRB in our ongoing studies using similar recruitment methods (Appendix).

For eligible Veteran patients who gave permission to the study team to contact their caregiver, a member of the study team will call the caregiver to describe the survey, answer questions, ascertain eligibility, and obtain informed consent. It will be common based on our experience with the RCT of HI-FIVES for the caregiver to answer the Veteran's phone. If this is the case, we will proceed to the caregiver informed consent and screening script (Appendix).

For caregiver surveys, we will seek a waiver of documentation of informed consent and HIPAA given that recruitment and data collection is entirely telephone based and minimal risk (Appendix). Participation is voluntary. The caregiver survey exclusion criteria by phone screening include:

- Unwilling to complete baseline survey and 3-month follow-up survey
- Not able to communicate via telephone
- Of minority age
- Caregiver is a professional without a pre-existing personal relationship with the Veteran and receives payment for caregiving services

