- Caregiver is a member of the Durham HSR&D Veteran and Family Input Initiative (VAFII), where members have advised and provided input towards the development of iHI-FIVES intervention materials (will apply to the Durham VAMC site only, study staff have a list of VAFII caregiver members).
- Informs us Veteran is currently in hospital or institution
- Informs us Veteran is currently receiving hospice care

The goal is to collect 120 surveys from caregivers in the pre-implementation period and 200 caregivers in the post-implementation period (n=320). All caregivers will fill out a baseline survey upon consent and 2-3 months later complete a follow-up survey. Both surveys take approximately 20-30 minutes to complete. The primary analysis approach for the caregiver outcomes (satisfaction with VA care, subjective burden, depressive symptoms), will be performed on these 320 caregivers.

For an "as treated" analysis, there will be an additional pool of caregivers recruited into the study among those participating in the iHI-FIVES clinical program. We expect that not every caregiver participating in the clinical program will consent to be a research subject, thus, with a conservative estimate of a 50% enrollment rate from the pool of participating caregivers (n=320), the minimum number of participating caregivers in the "as treated"

analysis is expected to be 100. Prior to the start of the first iHI-FIVES training, a member of the study team will call caregivers to ascertain eligibility and obtain verbal informed consent from the caregiver. Study team members will describe that participation in the study is completely voluntary and will not impact the caregiver's invitation to attend the iHI-FIVES training. Caregivers will be provided a toll-free number to contact if they do not wish to be contacted further. See Appendix for the caregiver informed consent script and screening script.

Rationale for Caregiver Enrollment and Screening over the Telephone. We have opted not to enroll caregivers of Veterans during the Veteran's hospital admission or other in-person visit to their VAMC for logistical reasons. A telephone-based strategy makes the evaluation possible by allowing enrollment of caregivers from multiple VAMCs across the country. To inform future implementation efforts, we will track number of attempts to contact and examine differences between caregivers who enrolled or refused and those we were unable to contact.

Caregiver Interviews.

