Based on the sample size, we may use only a subset of these matching variables, and use exact and distancematched methods. Candidate matching variables for the caregiver will include: age, race, employment status, education, and caregiver relationship to the Veteran. We will use the same analysis techniques for the "as treated" analysis as described above. Or we may simply use regression adjustment if sample size is too low, from the candidate set of covariates described here.

To address the value of iHI-FIVES from the caregiver's perspective, qualitative data will be collected via 15-20-minute semi-structured telephone interviews with a sample of caregivers who participate in iHI-FIVES. Interviews will be audio recorded. We will ask patients about whether they found iHI-FIVES to be helpful for them and in what ways and if they have suggestions for improvement. We will analyze data using conventional content analysis, in which we will transcribe interviews and then code text with descriptive labels that are developed as we read through transcripts. Data will be coded by a team process as described in Aim 1. Findings from Aims 1 and 2 will be supplemented by **budget impact analyses**.

Aim 3: To determine the conditions under which STRIDE implementation is most successful.

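### Caregiver surveys are taken at baseline and follow-up, but the caregiver model neither pre-specifies the baseline score as a covariate nor says which survey supplies the outcome

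*Combined protocol and SAP*

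**What the plan says.** **Data collected.** Under Sample of Caregivers (iHI-FIVES methods), two surveys per person are built into the design: "All caregivers will fill out a baseline survey upon consent and 2-3 months later complete a follow-up survey". Being unwilling to do both is an exclusion: "Unwilling to complete baseline survey and 3-month follow-up survey". The target is 120 caregivers before and 200 after implementation, 320 in all, and "The primary analysis approach for the caregiver outcomes (satisfaction with VA care, subjective burden, depressive symptoms), will be performed on these 320 caregivers".

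**Status.** The same section opens with "Survey data will be used to construct secondary caregiver outcomes". The word primary in the preceding quote therefore refers to the main analysis of secondary outcomes.

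**Model.** Aim 2b gives an example equation for a continuous outcome: a mean, a random site effect, a fixed period effect, an intervention indicator and an error term. On covariates it adds only "Adjustments for patient characteristics and a random effect for VAMC site may also be added". Negative binomial and logistic versions are provided for other outcome types.

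**Covariates named elsewhere.** The iHI-FIVES Key covariates paragraph lists patient and site variables. For the as-treated analysis, "Candidate matching variables for the caregiver will include: age, race, employment status, education, and caregiver relationship to the Veteran". Neither list contains a baseline burden, depression or satisfaction score.

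**Not stated.** The plan does not say whether the outcome is the follow-up score or the change from baseline, and does not list the content of either survey. It gives no power, SD, ICC or baseline/follow-up correlation for caregiver outcomes.

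**The concern.** A caregiver's own earlier score on the same scale usually predicts the later score well. Here each person is asked for both, yet the example model has no place for the first. The Aim 2b text closely follows the STRIDE text under Aim 2a. STRIDE patients are surveyed once, 30 days after discharge, so no baseline survey score exists there. The caregiver design has a baseline survey, but its model does not use it.

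Two things are at stake. The first is precision: 320 people at 8 sites, different people before and after the switch, compared with the full between-person variance left in the error term. The second is pre-specification: follow-up only, change, and baseline-adjusted follow-up can give different answers on three outcomes, and the plan leaves the choice open.

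**Working it through.** **1. The plan's own figures.** There is no caregiver power figure to reproduce. The 120/200 split can be checked. Suppose 10 caregivers per site-period, 8 sites, 5 periods, and the second block of four sites surveyed from period 3. This layout is inferred, because Figure 5 is not readable.
- Pre-implementation site-periods: 2×1 + 2×2 + 2×1 + 2×2 = 12, giving 120 caregivers.
- Post-implementation site-periods: 2×4 + 2×3 + 2×2 + 2×1 = 20, giving 200 caregivers.

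The total is 320, as stated.

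The only iHI-FIVES power statement concerns patient days not at home (400 Veterans, baseline mean 8, 2-day reduction, variance equal to the mean, CV 0.3-0.5, at least 80% power). The Hussey and Hughes variance with 8 sites × 5 periods × 10 gives an SE of 0.512-0.515. Power is Φ(2/0.512 − 1.96), about 97%, which is consistent with that lower bound. It says nothing about caregiver scores.

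**2. Inputs assumed for the caregiver outcomes (none is in the documents).** Baseline/follow-up correlation r = 0.3, 0.5, 0.7; site ICC 0 to 0.10; total SD 1; two-sided alpha 0.05; linear model; the same instrument in both surveys.

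**3. Formulas.** The variance of the effect is the Hussey and Hughes generalised least squares variance on the layout in step 1, with residual variance 1 − ICC and between-site variance ICC. Baseline adjustment multiplies the residual variance by (1 − r²) and leaves the site variance unchanged. The detectable effect at 80% power is (1.96 + 0.84) × SE.

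**4. Without the baseline score.** The SE runs from 0.149 (ICC about 0) to 0.176 (ICC 0.10), so the detectable effect is 0.42 to 0.49 SD.

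**5. With the baseline score.**

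| r | Effect variance multiplied by | Detectable effect at 80% power (SD) | Power for an effect that had 80% unadjusted |
|---|---|---|---|
| 0.3 | 0.91-0.92 | 0.40-0.47 | 83-84% |
| 0.5 | 0.75-0.78 | 0.36-0.43 | 89-90% |
| 0.7 | 0.51-0.56 | 0.30-0.36 | 96-98% |

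**6. Equivalent sample size, clustering ignored.** 320/(1 − r²): 320/0.91 = 352; 320/0.75 = 427; 320/0.51 = 627.

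**7. A change score is not an equivalent remedy.** With equal variances at the two surveys, its variance factor is 2(1 − r): 1.4 at r = 0.3, 1.0 at r = 0.5 and 0.6 at r = 0.7. The adjusted factors are 0.91, 0.75 and 0.51.

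**8. The possible cost.** If the mean post-period baseline has already moved by a fraction f of the true effect, the adjusted estimate shrinks by about r × f. With f = 0.3 (illustrative; the documents give no value), this is 0.3 × 0.3 = 9%, 0.5 × 0.3 = 15% or 0.7 × 0.3 = 21%.

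**The case against.** The strongest reply is that the baseline is not cleanly pre-exposure. For the 320, it is taken at consent. In the post period the site has already switched, the referral may be 3 or 6 months old, and at least two class rounds run every six months. Consent before the first training is described only for the separate as-treated pool. A covariate measured after exposure in one condition only can absorb part of the effect, as step 8 shows. This stands, and it is why the change is cheap but not free. A reader might infer that only a small group is affected. The documents give no size for it.

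A reader might also think that dropping post-period caregivers who attended a class before baseline would settle the matter. It would not. That removes self-selected early attenders from one condition, with no counterpart to remove before implementation.

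Other points that stand:
- The equation is an example and covariates may be added. A reader might infer that baseline adjustment is ruled out; it is only not pre-specified.
- A reader might infer that the stated model is exposed to secular drift in starting burden or depression. The fixed period effect absorbs shifts common to all sites. What remains is between-person variance and site-specific differences in who was sampled.
- Sampling different people before and after is normal in a stepped wedge of this kind and is not a defect.
- That all three scores are in both surveys is a reasonable inference, but the documents do not state it.
- The figures in steps 5 and 6 apply to the linear model, not directly to the negative binomial or logistic versions.

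**Conclusion.** The point holds as an avoidable loss of precision and a gap in pre-specification for the secondary caregiver outcomes. Adjusting the follow-up score for the baseline score gains precision in the linear model at any non-zero correlation. The gain is modest at r = 0.3 (variance down 8-9%), useful at 0.5 (22-25%) and large at 0.7 (44-49%), for a site ICC of 0 to 0.10. All of these correlations and ICCs are assumptions. The equivalents of 352, 427 or 627 caregivers also ignore clustering, so the upper figures should not be read as an expected gain.

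The benefit has to be weighed against possible attenuation where baseline followed class attendance, which cannot be sized from the documents. A reader might infer that the trial's main conclusion is at risk. It is not: the primary iHI-FIVES outcome is Veteran days at home, from administrative data.

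**What to change.** In the Aim 2b analysis text:
- Name the follow-up score as the outcome for burden, depressive symptoms and satisfaction.
- Pre-specify the same instrument's baseline score as a covariate in the 320-caregiver model and in the as-treated model, after confirming that it is in both surveys.
- Record from the attendance logs whether each post-period baseline survey preceded any class, and report how many did not.
- Report the model without baseline adjustment as the sensitivity analysis, rather than relying on excluding early attenders from the post period only.

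Label: cheap improvement. The cost is a few sentences in the plan and one timing flag. The baseline and follow-up surveys and the attendance logs are already planned, so no new outcome data are needed. The remaining downside is attenuation where baseline followed a class. The flag shows how common that is, and comparing the adjusted and unadjusted results shows how far the adjustment moves the estimate.
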